8. ABBREVIATIONS

AAo – ascending aorta
AVOA – amplitude of aortic valve opening
AML – anterior mitral leaflet
Ao – aorta
AoArch – aortic arch
AoRoot – aortic root
AoV – aortic valve
AR – aortic regurgitation
AS – aortic stenosis
ASA – atrial septal aneurysm
ASD – atrial septal defect
ASE – American Society of Echocardiography
AVA – aortic valve area
BSA – body surface area
CFD – color flow Doppler
CI – cardiac index
CO – cardiac output
CS – coronary sinus
CWD – continuous wave Doppler mode
DAO – descending aorta
EDV – end-diastolic volume
EF – ejection fraction
EPSS – E point to septal separation of the mitral valve
ESV – end-systolic volume
A5CV – apical five-chamber view
A4CV – apical four-chamber view
IVC – inferior vena cava
IVS – interventricular septum
LA – left atrium

LAA – left atrial appendage
LAX – long axis
LAX Ao – longitudinal section of the aorta
LAX LV – longitudinal section of the left ventricle
LAX RVIT – longitudinal section of the right ventricular inflow tract
LAX RVOT – longitudinal section of the right ventricular outflow tract
LCC – left coronary cusp
LPA – left pulmonary artery
LV – left ventricle
LVEF – left ventricular ejection fraction
LVIDd – left ventricular internal diameter in diastole
LVIDs – left ventricular internal diameter in systole
LVIDV – left ventricular internal diastolic volume
LVISV – left ventricular internal systolic volume
LVOT – left ventricular outflow tract
LVPW – inferolateral wall of the left ventricle
M-mode – M-mode
MR – mitral regurgitation
MS – mitral stenosis
MVA – mitral valve area
NCC – non-coronary cusp
PA – pulmonary artery
PAP – pulmonary artery pressure
PG – pressure gradient
PHT – pressure half-time
PML – posterior mitral valve leaflet
PR – pulmonary regurgitation
PS – pulmonary stenosis
PV – pulmonary valve
PWD – pulsed wave Doppler mode
RA – right atrium
RAP – right atrial pressure
RVWT – right ventricular wall thickness
RVIT – right ventricular inflow tract
PTCL- V 1.1

RVOT – right ventricular outflow tract

RVSP – right ventricular systolic pressure

SAM – systolic anterior motion

SAX APEX – short axis at the apex level

SAX BASE – short axis at the base level

9. INTRODUCTION

9.1 Introduction and Research Hypothesis

During surgical intervention for aortic valve insufficiency accompanied by hemodynamically significant functional mitral regurgitation, the surgeon faces the question of whether intervention on the mitral valve is necessary. Secondary MR of varying degree is found in 60%-75% of patients who have undergone aortic valve replacement. [1]

We hypothesize that the chosen strategy regarding moderate mitral regurgitation during the correction of aortic valve lesion in patients with significant left ventricular remodeling plays a crucial role in the course of reverse LV remodeling when assessed by transthoracic echocardiography 12 months post-surgery.

9.2 General Information

Adaptation of the cardiovascular system to increased preload is observed in a number of quite physiological conditions: child growth, pregnancy, intensive aerobic training, as well as in pathological processes: atrioventricular valve insufficiency, or systemic arteriovenous shunt. [2, 3]

9.3 Study Rationale

The heart is a terminally differentiated organ with very limited reparative capabilities at the cellular level. The number of heart cells does not change over a lifetime; according to some data, the volume of cellular repair does not exceed 1% of the cellular mass per year. Cardiomyocytes are incapable of completing mitosis due to the presence of a rigid cytoskeleton and, consequently, the impossibility of cytokinesis. Repair and compensation at the cellular level with the inability of cytokinesis involves a multiple increase in intracellular elements without completed division, which causes an increase in cytoskeleton stiffness. Aortic valve insufficiency is the third most common valvular heart defect. Severe and significant aortic valve insufficiency is associated with hemodynamically significant functional mitral valve insufficiency in more than one-third of cases. Aortic valve insufficiency should be considered pathogenetically and hemodynamically as a pressure and volume overload, while mitral regurgitation is a typical variant of isolated volume overload. Pressure overload causes cardiomyocyte hypertrophy due to the parallel layering of sarcomeres and disruption of energy couplings. Subsequent metabolic changes induce apoptosis and autophagy of cardiomyocytes with a progressive loss of functional cardiac cell mass; in the remaining functional

cardiomyocytes, polyploidization occurs, and simultaneously, a humoral response arises, the prolonged tension of compensatory mechanisms of which leads to worsening myocardial dysfunction. With volume overload, there is a progressive expansion of the left ventricular cavity due to the addition of new sarcomeres in sequence with the existing ones. Prolonged existence of volume overload also ultimately leads to the loss of functional cardiac cell mass and the development of systolic and diastolic heart failure. It should be noted that the elongation of the left ventricular cross-sectional circumference along the short axis due to progressive dilation, according to the Frank-Starling law, requires supraphysiological preload to achieve optimal contraction strength. Functional mitral regurgitation is a variant of increased preload. A sharp decrease in left ventricular preload with hemodynamically effective correction of functional mitral regurgitation simultaneously with the correction of the aortic defect can potentially impair left ventricular contractility in the early stages of reverse remodeling. It is evident that postoperative regression of mitral regurgitation is possible in cases where the reverse development of changes that caused mitral regurgitation is possible. For example, with normal sizes of the left ventricle and atrial tethering of the mitral valve against the background of persistent atrial fibrillation, isolated correction of aortic valve insufficiency is not able to reverse the arrhythmogenic fibrosis of the left atrium and, consequently, improve the grading of mitral regurgitation. Mitral regurgitation against the background of a significant increase in the end-systolic size of the left ventricle and a decrease in contractility may be characterized by a favorable prognosis of reverse development after correction of the aortic defect, provided there are no other causes of mitral regurgitation.

There is a limited number of research studies dedicated to the reverse remodeling of the left ventricular myocardium and the spontaneous regression of functional mitral regurgitation after surgical correction of aortic stenosis; the degree of study of this issue in the context of aortic valve insufficiency is even lower. In the available studies, the main focus is on assessing the impact of hemodynamically significant functional mitral regurgitation, which has not undergone surgical correction during aortic valve replacement, on immediate and long-term survival, as well as the course of the mitral regurgitation itself. In many studies, fundamentally different causes of functional mitral regurgitation—such as aortic stenosis and aortic valve insufficiency—are not distinguished. None of the studies found evaluate the course of reverse remodeling of the left ventricle depending on the chosen strategy regarding the mitral valve. The obtained results and conclusions on the aforementioned issues are contradictory, exacerbating the ambiguity of the scarce data. There are also no studies that include patients exclusively with severe forms of left ventricular remodeling against the background of chronic aortic regurgitation. The duration of hemodynamically significant aortic valve insufficiency and the age of manifestation, as well as the patient's gender, are rarely analyzed. Thus, the study of reverse remodeling of the left ventricular myocardium in patients with chronic aortic valve insufficiency against the background of functional mitral regurgitation is of interest, remains unexplored, and is clinically relevant.

10. OBJECTIVES AND ENDPOINTS OF THE STUDY

To study the impact of the volume of surgical treatment for chronic aortic valve insufficiency on the rate and degree of reverse myocardial remodeling in patients with significant left ventricular dilation against the background of chronic aortic regurgitation, depending on the degree of mitral valve insufficiency.

10.1 Objectives

Primary objective:

1. To assess the impact of functional mitral regurgitation on the rate and degree of reverse myocardial remodeling in patients with significant left ventricular dilation against the background of chronic aortic valve insufficiency after surgical correction of the aortic defect.

Secondary objectives:

1. To assess the relationship between the severity of preoperative functional mitral valve insufficiency and the patient's life quality 12 months after surgery.

Research objectives:

1. To assess the relationship between severity of functional mitral regurgitation and diastolic dysfunction of the left ventricle at 3 and 12 months after surgical correction of aortic regurgitation.
2. To assess the relationship between the severity of functional mitral regurgitation and the dynamics of left atrial volume, evaluated by transthoracic ECHO-CG, at 3 and 12 months after surgical correction of aortic regurgitation.

10.2 Study endpoints

Primary endpoints:

1. *Reduction of the left ventricle end-diastolic volume at 3 and 12 months after surgical correction of aortic regurgitation*
2. *Freedom from readmission for heart failure related conditions 12 months after surgery*

Secondary endpoints:

1. Patient quality of life according to the EQ-5D-5L questionnaire results.

Exploratory endpoints:

1. Left ventricle ejection fraction at 3 and 12 months after surgical correction of aortic regurgitation

2. Diastolic function of the left ventricle based on echocardiography results, assessed preoperatively and at 3 and 12 months after surgical correction of the aortic regurgitation (mean E/e', DT)
3. Indexed to BSA volume of the left atrium (according to transthoracic echocardiography results) preoperatively, as well as at 3 and 12 months after surgical treatment

*BSA – body surface area, calculated using the Mosteller formula

11. Study design

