Investigated procedure	
It is planned to study the initial and long-term results of left ventricle reverse remodeling in patients with aortic regurgitation, depending on the strategy chosen for the correction of functional mitral regurgitation and its severity.

Duration of observation	12 months after surgical treatment
Methods of statistical evaluation	
The determination of the significance of differences between quantitative data of unrelated samples will be carried out using the Student's t-test under the condition of normal distribution; in the case of non-normal distribution, the Mann-Whitney test, White's test, Van der Waerden test, and Kolmogorov-Smirnov test are planned to be used. In the case of analyzing the significance of differences in quantitative data in related samples with a normal distribution, the paired Student's t-test is planned to be used; in the case of non-normal distribution, the Wilcoxon test and sign test will be used. Qualitative data analysis will be performed using the χ^2 test and the McNemar test. To assess the reliability of the relationship between quantitative data, regression analysis, Pearson's correlation coefficient, Spearman's rank correlation coefficient, and Kendall's correlation coefficient are planned to be used. Descriptive and analytical statistical methods will be finalized after analyzing the sample size. To eliminate the influence of differences in baseline clinical parameters on the study outcome, a propensity score matching analysis (PSM) is planned between the ordinary 'Unmatched' groups using the nearest neighbor matching method for 1:1 pair matching.
 
Demographic data and clinical indicators will be presented using descriptive statistics (absolute indicators and percentage shares for categorical variables, or mean \pm standard deviation for normally distributed continuous variables; for continuous variables with non-normal distribution, the median and interquartile range will be specified). The significance of differences in repeated measurements will be analyzed using ANOVA.

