Sample size	
Considering a clinically significant difference in left ventricle volumes 12 months after surgery, equal to 15 ml/m^2, with a power of 80% and alpha of 5%, the sample size should be at least 64 patients in each group.
 
The sample size usually depends on the standard deviation, which is determined based on the results of similar studies or, more often, a pilot study. Approximate indicators will be obtained by February 2024 after analyzing the RCHC sample within the framework of the dissertation research.

--------------------	---

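### The sample size and its 5% alpha cover one BSA-indexed left ventricular volume at 12 months, but the primary endpoints are unindexed EDV reduction at 3 and 12 months plus an unsized readmission endpoint

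*Protocol*

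**What the plan says.** **Endpoints (Protocol 10.2).** Two numbered primary endpoints are listed: "Reduction of the left ventricle end-diastolic volume at 3 and 12 months after surgical correction of aortic regurgitation" and "Freedom from readmission for heart failure related conditions 12 months after surgery". The first carries two time points and no indexing. In the same section an exploratory endpoint is expressly indexed, "Indexed to BSA volume of the left atrium", and a footnote defines BSA as "body surface area, calculated using the Mosteller formula". The inclusion criterion (11.2.1) also uses EDV in absolute terms, 250 ml or more.

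**Sample size (Protocol 7, synopsis).** One calculation is given. It rests on a "clinically significant difference in left ventricle volumes 12 months after surgery" of 15 ml/m², and concludes that "with a power of 80% and alpha of 5%, the sample size should be at least 64 patients in each group". No standard deviation is given. Nothing is sized for 3 months or for readmission.

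**Methods (Protocol 7, synopsis).** For unrelated samples the t-test is named under normality. Otherwise "the Mann-Whitney test, White's test, Van der Waerden test, and Kolmogorov-Smirnov test are planned to be used". Repeated measurements go to ANOVA, and 1:1 propensity score matching is planned.

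**Time point.** The hypothesis in 9.1 refers to 12 months. The synopsis objectives compare 3 and 12 months, and the primary objective in 10.1 covers both the rate and the degree of remodeling.

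**The concern.** A sample-size statement promises a given power at a given error rate for a named primary result. Here the sized quantity and the primary endpoints differ in three ways: indexed against unindexed, one time point against two, and one outcome against two. A reader cannot tell in advance which p-value carries the 5%, or whether the 80% belongs to the whole primary set. The list of non-normal tests adds a smaller version of the same problem, because several tests address one comparison and none is marked as deciding.

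**Working it through.** **1. Sized quantity against primary set**

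| | Sample-size paragraph | Section 10.2 |
|---|---|---|
| Quantity | left ventricular volume | EDV reduction; readmission |
| Unit | ml/m² | EDV not indexed |
| Time | 12 months | EDV at 3 and 12; readmission at 12 |
| Alpha | one, 5% | no allocation stated |

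The unit gap is not small. For an assumed BSA of 1.7 to 2.1 m² (the protocol gives none), 15 ml/m² is 15 × 1.7 = 25.5 ml to 15 × 2.1 = 31.5 ml.

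**2. The plan's own figure**

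n per group = 2(z₀.₉₇₅ + z₀.₈₀)²(SD/Δ)². No SD is given, so 64 cannot be reproduced from the protocol alone. With an assumed SD of 30 ml/m² and a two-sided test: 2 × (1.960 + 0.842)² × (30/15)² ≈ 62.8, so 63. The t-test solution is 63.8, so 64. Working back from 64 per group, the standardized difference is d = 0.499. The figure thus fits one two-sided, unpaired comparison at the full 5%.

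**3. Error rate if any one result counts as success, each at two-sided 5%**

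- Two independent comparisons (the EDV times joined in the ANOVA, plus readmission): 1 − 0.95² = 9.75%.
- Three independent comparisons: 1 − 0.95³ = 14.3%.
- Three comparisons, with the 3- and 12-month EDV results correlated (assumed ρ) and readmission independent: 1 − (1 − pair error) × 0.95.

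| ρ | EDV pair | All three |
|---|---|---|
| 0.3 | 9.5% | 14.0% |
| 0.5 | 9.1% | 13.6% |
| 0.7 | 8.3% | 12.9% |
| 0.9 | 7.1% | 11.7% |

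Whatever the dependence, the upper bounds are 2 × 5% = 10% and 3 × 5% = 15%.

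**4. If alpha were split equally instead**

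With d = 0.499 and a t-test, 80% power for the sized volume needs 78 per group at 0.05/2 and 86 at 0.05/3. At 64 per group (d = 0.5), power falls from 80% to 71% and 66%.

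**5. If all must succeed**

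There is no inflation, but overall power cannot exceed that of the weakest component. At 64 per group, readmission has 35% power for assumed rates of 20% v 10%, 47% for 15% v 5%, and 73% for 20% v 5%.

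**6. Test list**

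Null simulations covered Mann-Whitney, Van der Waerden and Kolmogorov-Smirnov. White's test was treated as the same rank-sum statistic as Mann-Whitney, so it adds nothing. The probability that at least one test has p < 0.05 was 6.7-7.4% for 45 to 64 per group (200,000 permutations per size). A separate simulation with skewed data at 64 per group gave 7.0%, against 3.6% to 5.3% for each test alone.

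**The case against.** - **A separate SAP may settle multiplicity and name one test.** This stands. The absence of an alpha rule from the protocol is not in itself an error, and the sentence "Descriptive and analytical statistical methods will be finalized after analyzing the sample size" may point to such a document. A SAP would not remove the mismatch between section 10.2 and the sample-size paragraph, because the protocol states both.
- **There are two numbered primaries, and ANOVA can take both EDV times together.** This is a fair reading, so the two-comparison figure is given beside the three-comparison one.
- **A reader might infer that the trial runs at a 14% error rate.** The protocol does not support that. It never says that any one result suffices, and the figures in step 3 hold only under that rule.
- **A reader might infer that the smallest of four p-values may be reported.** No text permits this. The list also applies only to the non-normal branch and covers quantitative data in general. What stands is that it names several tests for one comparison and no deciding one.
- **A reader might infer that the sized volume is unidentifiable, or that 15 ml/m² cannot be related to the data.** That goes too far. EDV is the only left ventricular volume among the endpoints, sizing and hypothesis both point to 12 months, and indexed EDV is in the echo protocol (Appendix 2). The gap is one of definition, not of data.

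**Conclusion.** The point holds as a mismatch inside the protocol. The study is sized once, at 5%, on an indexed 12-month volume. Its primary set is unindexed EDV reduction at two times plus an unsized readmission endpoint. The stated 80% power and 5% alpha do not describe that set.

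The consequence depends on a decision rule the protocol does not give: about 10% (two comparisons) or about 12-14% (three) if any one result suffices, or no inflation but lower power if all must succeed. Choosing the smallest p-value from the test list would give about 7% for one comparison. These figures assume two-sided 5% tests, readmission independent of volume, and correlations of 0.3 to 0.9 between the EDV times for the three-comparison range. The sample sizes rest on an effect size worked back from 64, since no SD is given.

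This should be corrected, but it does not undermine the design. The planned total of 120 against 2 × 64 = 128 is a separate point and plays no part here.

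**What to change.** 1. **Section 10.2:** name the reduction from baseline to 12 months in BSA-indexed left ventricular EDV as the single primary endpoint.
2. **Sample-size paragraph:** say that the 15 ml/m² is the between-group difference in this reduction, and take the SD for the same quantity.
3. **Remaining primaries:** make the 3-month indexed EDV reduction and readmission secondary. Alternatively keep them primary in a fixed sequence: 12-month indexed EDV reduction, then 3-month, then readmission, each at 5% only if the step before succeeded. Either way the sized endpoint keeps the full 5%, so multiplicity does not raise the 64 per group.
4. **Methods paragraph:** replace the four-test list for the primary comparison by one deciding test, chosen before outcome data are seen. It must be consistent with the matched or unmatched design and with the sample-size calculation. Any other test is a sensitivity analysis.

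**Cost:** one amendment, agreed in writing with the principal investigator and the ethics committee (15.1). No new data are needed: indexed EDV is in Appendix 2, and height and weight are taken at Examinations 1, 4 and 5 (12.4.4). The downside is that the 3-month volume and readmission lose primary status, or can be claimed only after the earlier step succeeds. The 3-month result still serves the objective on rate of remodeling.

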7. PROTOCOL SYNOPSIS

Study Title	Assessment of the left ventricle reverse remodeling outcomes in patients with aortic valve insufficiency after surgical correction
Sponsor	Investigator-Initiated Study
Study Phase	Phase III
Hypothesis	We hypothesize that surgical correction of functional mitral regurgitation during interventions for chronic aortic valve insufficiency in patients with significant dilatation of the left heart chambers affects the reverse remodeling of the left ventricle in the postoperative period.

Research objectives and tasks	
Research objective:
 
To assess myocardial reverse remodeling in patients with significant left ventricular dilation caused by chronic aortic regurgitation, depending on the degree of mitral valve insufficiency and surgical approach.
 
Main objectives of the study:
 
1. To evaluate the short-term and long-term outcomes of aortic valve replacement for aortic valve insufficiency in patients with significant left ventricular dilation2. To compare the results of myocardial reverse remodeling depending on the strategy regarding functional mitral valve insufficiency at 3 and 12 months post-surgery3. To determine preoperative predictors of an unfavorable left ventricle function and architecture recovery prognosis.4. Assess the patients life quality 12 months after surgery5. Develop a clinical protocol for simultaneous surgical treatment of mitral regurgitation during aortic valve replacement in patients with significant left ventricular myocardial remodeling caused by chronic aortic regurgitation
Study design	This study is a multicenter, comparative, prospective

Inclusion criteria	
1. Age over 18 years2. Proposed primary elective surgical intervention for chronic aortic regurgitation3. Presence of functional mitral regurgitation4. Left Ventricular End-Diastolic Volume 250 ml\geq
Exclusion criteria	
1. Infectious endocarditis2. Previous myocardial infarction3. Necessity for simultaneous myocardial revascularization4. Acute aortic regurgitation5. Previously established left ventricular dilation not associated with the development of aortic regurgitation6. Lack of informed consent
Number of study subjects	120 patients

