SAX BASE (CWD)	TV Vmax TR Vmax TVA PV Vmax PV Gmax PV Gmean PVA EDPR	
 • Tricuspid stenosis • Tricuspid regurgitation • Pulmonary stenosis • Pulmonary regurgitation • RVOT obstruction 	
SAX BASAL/MV (2D)	MVA (planimetry)	
 • Prolapse/elongation of leaflets. • Myxomatous/thickening/calcification with/without restriction of excursion. • Local contractility disorder at the basal level 	 

Study protocol

SAX LV (MID/APEX) (2D)		Hypo-, a-, dyskinesia of the walls. Dilation of the right ventricle	
---------------------------------------	--	--	--

Study protocol

A4CV (2D)	
EDVi ESVi EF LV LAVi RVD1 RVD2 RAsax RALax RAA RAVi
 
Normal values: EDVi (female <61 ml/m², male <74 ml/m²) ESVi (female <24 ml/m², male <31 ml/m²) EF LV (female >52%, male >54%) LAVi (<34 ml/m²) RVD1 (25-41 mm) RVD2 (19-35 mm) RALax (<53 mm) RAsax (<44 mm) RAA (<18 cm²) RAVi (female 15-27 ml/m², male 18-32 ml/m²)
 
Note: LAV is calculated using the disk summation method RAV is calculated using the area-length method
		
A4CV (M-mode)	
TAPSE
 
Normal value: TAPSE >17 mm
	
Right ventricular dysfunction
	

A4CV (CFD)		
• Mitral stenosis• Mitral regurgitation• Tricuspid stenosis• Tricuspid regurgitation• Atrial septal defect• Ventricular septal defect	
A4CV (PWD)	VE MV VA MV E/A MV DT MV Adur VE TV VA TV E/A TV DT TV S D ARdur	
• Diastolic dysfunction of the left ventricle• Diastolic dysfunction of the right ventricle 
Normal values: E/A MV 1.0-1.5 DT MV 160-220 msec S>D AR<150 msec Adur<ARdur
	
A4CV (CWD)	MV Vmax MR Vmax MVA TV Vmax TR Vmax TVA RVSP/SPAP	
• Mitral stenosis• Mitral regurgitation• Tricuspid stenosis• Tricuspid regurgitation• Pulmonary hypertension	

Study protocol

A4CV (TDI PW)	e' lat E/e' lat e' med E/e' med E/e' avg	Diastolic dysfunction of the left ventricle Normal values: e' lat >10 cm/s e' med >7 cm/s E/e' lat <13 cm/s E/e' med <15 cm/s E/e' avg <14 cm/s	
A5CV (2D)		
• Mitral stenosis• SAM with/without LVOT obstruction• Aortic sclerosis/stenosis• Dilation of chambers• Local contractility of the ventricular walls	
A5CV (CFD)		
• LVOT obstruction• Mitral stenosis• Mitral regurgitation• Aortic stenosis• Aortic valve insufficiency• Ventricular septal defect	

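### Mean E/e' and DT are read at the mitral valve, so they are not comparable between patients with and without mitral correction, and exploratory endpoint 2 cannot separate procedure effect from diastolic function

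*Protocol*

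**What the plan says.** - **Endpoint.** Protocol 10.2, exploratory endpoint 2: "Diastolic function of the left ventricle based on echocardiography results, assessed preoperatively and at 3 and 12 months after surgical correction". The same item names the indices: "at 3 and 12 months after surgical correction of the aortic regurgitation (mean E/e', DT"). No other index is named under this endpoint, and no restriction by mitral procedure is stated.
- **Linked objective.** Protocol 10.1, research objective 1: "To assess the relationship between severity of functional mitral regurgitation and diastolic dysfunction of the left ventricle at 3 and 12 months". The exposure there is MR severity, not mitral strategy.
- **Exposure.** The hypothesis in the synopsis (section 7) concerns "surgical correction of functional mitral regurgitation during interventions for chronic aortic valve insufficiency". The investigated-procedure entry studies remodeling "depending on the strategy chosen for the correction of functional mitral regurgitation and its severity". Main objective 2 compares remodeling "depending on the strategy regarding functional mitral valve insufficiency at 3 and 12 months post-surgery", which are the visits at which E/e' and DT are taken.
- **Where the indices are read.** In Appendix 2 (22.2), mitral E and DT are in the apical four-chamber pulsed-wave row, with the reference range "DT MV 160-220 msec". The tissue Doppler row gives lateral and medial e' and their averaged ratio: "Diastolic dysfunction of the left ventricle Normal values: e' lat >10 cm/s e' med >7 cm/s". Its reference value for averaged E/e' is below 14.
- **Adjustment.** The synopsis plans 1:1 nearest-neighbour propensity matching, aimed at differences in baseline clinical parameters.

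**The concern.** The exposure acts on the structure at which the outcome is measured. A mitral procedure can change the inflow orifice, and with it E and DT, and can restrain the annulus, and with it e'. Where MR is left uncorrected, the regurgitant volume crosses the valve again in diastole and affects E. Two patients with identical LV relaxation and filling pressure can therefore have different E/e' and DT because one valve was operated on and the other was not.

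A between-strategy difference in these indices would then have no clear meaning: it could be myocardial, procedural or both. Objective 1 could be affected as well. If more severe MR is corrected more often, an association between severity and postoperative E/e' may be partly an association with the procedure.

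**Working it through.** The plan gives no figure on this point. Its only calculated number, the sample size, concerns LV volume. The check is therefore whether the passages create the problem, and then what range of distortion is possible.

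**1. Reading the passages together**

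| Question | Source | Answer |
|---|---|---|
| Which indices define diastolic function? | 10.2 | Mean E/e' and DT only |
| Where are they read? | Appendix 2 | Mitral inflow; lateral and medial tissue Doppler |
| Is that valve operated on in some patients? | Section 7 | Yes, this is the strategy under study |
| Does loading differ by strategy? | 9.3 and 11.1 | Yes: effective correction lowers LV preload markedly; residual MR raises it |
| What does the adjustment cover? | Section 7 | Baseline differences only |

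Matching balances patients before surgery. A measurement change that arises at surgery is not a baseline difference, so perfect matching would leave it in place.

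**2. Algebra for E/e'**

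Let s be the relative change in E and r the relative fall in e'. Then

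(E/e' after) / (E/e' before) = (1 + s) / (1 - r).

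The ratio rises only if s > -r, that is, if E falls proportionally less than e'. The documents give neither s nor r, so every value below is an assumption.

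**3. One worked case.** Assume E = 80 cm/s and e' = 8 cm/s, so E/e' = 80/8 = 10.0. Let e' fall to 7 cm/s (r = 1/8 = 12.5%).

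| Assumed change in E | E/e' after |
|---|---|
| +50% | 120/7 = 17.1 |
| +25% | 100/7 = 14.3 |
| 0 | 80/7 = 11.4 |
| -12.5% | 70/7 = 10.0 |
| -20% | 64/7 = 9.1 |

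The sign changes at a 12.5% fall in E.

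**4. Wider range**

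- r = 20%, s = -30%: 0.70/0.80 = 0.875.
- r = 20%, s = 0: 1.00/0.80 = 1.25.
- r = 20%, s = +20%: 1.20/0.80 = 1.50.
- Lowest corner, r = 0 and s = -30%: 0.70/1.00 = 0.70.
- Highest corner, r = 30% and s = +30%: 1.30/0.70 = 1.86.

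From a starting value of 10, the corners are 7.0 and 18.6, with no change in relaxation or filling pressure.

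**5. DT.** The documents support no calculation. The reference range is two-sided, so a shift has no single adverse direction.

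**The case against.** **Direction.** A reader might infer that mitral correction will look like worse diastolic function, because a ring or prosthesis raises E and lowers e'. The documents do not support that. Section 9.3 says effective correction cuts LV preload sharply, which could lower E. Section 11.1 says residual MR raises preload in the uncorrected group. The working shows that the sign depends on which change is larger. Nor does exceeding 14 have a planned consequence: it is a reference value in the appended echo protocol, not an endpoint threshold.

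**Missing facts.** The type of mitral procedure, the share of patients receiving it and its effect on E, e' and DT are not stated. That a procedure alters these readings is general measurement reasoning, not protocol text. This limits any claim about size, but it does not make the indices comparable.

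**Scope.** Objective 1 concerns MR severity, and the strategy comparison in main objective 2 is stated for remodeling without naming diastolic function. The carry-over to objective 1 is therefore conditional on severity and correction being linked. That is plausible, but no allocation rule is given.

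**SAP.** Stratification and analysis sets commonly sit in an SAP, which is not shown. That is fair for the analysis detail. The choice of two mitral-dependent indices as the whole content of the endpoint is, however, fixed in the protocol.

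**Restriction is not a clean remedy.** Limiting objective 1 to unoperated patients would select on treatment, could truncate the severity range under study, and would leave the effect of residual MR on E. TR Vmax/RVSP and pulmonary venous flow also respond to MR. This stands, and it shapes the fix.

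**Conclusion.** The point holds in a limited form. As defined, exploratory endpoint 2 cannot separate the effect of a mitral procedure from LV diastolic function, and E/e' and DT are not comparable between patients with and without mitral correction. Baseline matching does not help. Objective 1 may be partly confounded if MR severity and correction go together.

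The sign and size of the bias are unknown. The multiplier of 0.70 to 1.86 for E/e' rests wholly on assumed changes in E and e', and shows only that the distortion could be material in either direction. The conclusion assumes that some patients do have the mitral valve operated on, as the hypothesis implies, and that the operation can affect inflow or annular motion.

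The weight is modest. One exploratory endpoint is affected; the primary endpoints, quality of life and the sample size are not. It is still worth correcting, because a between-strategy result would otherwise be uninterpretable and the change is cheap.

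**What to change.** In Protocol 10.2, under exploratory endpoint 2:

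1. Analyse and report mean E/e' and DT at 3 and 12 months separately by mitral procedure (none or performed, and by type if more than one is used). Treat them as descriptive in operated valves.
2. State that a between-strategy difference in E/e' or DT will not be interpreted as a difference in diastolic function.
3. Stratify research objective 1 by mitral procedure rather than dropping operated patients.
4. For comparisons across strategy, add TR Vmax/RVSP, already among the Appendix 2 measurements, and read it alongside indexed left atrial volume, already exploratory endpoint 3. Report both with residual MR grade at the same visit, because they also respond to MR and are supportive rather than free of the problem.

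Cost: wording only, with no new visit or imaging modality. The strata are smaller, so an exploratory endpoint is estimated less precisely.
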